| Title | Effects of Transcranial Alternating Current Stimulation (tACS) on Memory Recall and Sleep-EEG in Healthy Elderly Participants (SUPERCHARGE) |
| Study Description | 
The purpose of this clinical trial is to investigate the feasibility and efficacy of non-invasive transcranial alternating current stimulation (tACS) at gamma frequency in enhancing memory recall and modulating sleep network dynamics measured by at-home electroencephalography (EEG) in healthy elderly people. Eligible participants will first collect sleep EEG at home for one night to acclimate to the data collection during sleep. Participants are then randomized into first undergoing either gamma-tACS or control tACS. Stimulation is administered in the lab during a cognitive testing battery that includes memorizing items. After a night of sleep with EEG at home, participants return to the lab the following day to measure memory recall. Memory recall is tested again by telephone five days later. This sequence of encoding during stimulation in the lab, sleep EEG at home for one night, and memory recall is then repeated for the other stimulation condition about a week later. An actigraphy watch (accelerometer) is worn during the whole study period.
 |

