During stimulation, the participants will perform the following cognitive tests presented on the computer screen or on paper: RAVLT (Rey Auditory Verbal Learning Test) (26), a word association test (8 word-pairs), Letter Fluency (28), Stroop Color and Word Test (29), Trail Making Test A and B (30), TAP (Test of Attentional Performance) (31). The stimulator will be triggered by remote control from the experiment script and will administer stimulation during each single test. After each block of stimulation, an eyes-open resting state EEG will be performed. All stimulation involves 20 seconds of ramp-in time and 20 seconds of ramp-out time. The total duration of the stimulation and testing is approximately 40 minutes.

7. Schedule of Activities and Procedures

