8.3 Aim-Specific Plans

Plans for Aim 1.

a) The proportion of participants in which stimulation and cognitive testing could be completed will be calculated after both stimulation sessions, i.e. visit 2 and visit 4 (percentage and 95% confidence interval).

Plans for Aim 2.

To evaluate the effect of gamma-tACS on cognitive testing.

a) Primary outcome: Ultra-delayed verbal memory recall (i.e. amount of words and word associations remembered the day after encoding the RAVLT) after gamma-tACS compared to after control stimulation, intra- and interindividually.

We will perform a two-way or one-way repeated measure ANCOVA with time (baseline and post-treatment) and treatment (control vs gamma-tACS) as within-subjects factors, and the order in which tACS will be applied (tACS-sham or control tACS) as covariate. Post-hoc tests will be calculated after Bonferroni correction for multiple comparisons.

Null hypothesis: There is no difference between tACS and control stimulation for ultra-delayed memory recall one day after stimulation. Alternative hypothesis: Memory recall is better after gamma-tACS than after control stimulation.

b) Secondary outcomes: Verbal and associative learning (immediate and delayed recall, recall after 5 days) and executive functions (results of Letter Fluency, Stroop Test, Trail Making Test, Tests of Attentional Performance), comparison intra- and interindividually, after gamma-tACS and control stimulation (comparison of difference

between visit 1-visit 2 and visit 3-visit 4; comparison of absolute results of visit 1 versus visit 3 and visit 2 versus visit 4; statistical tests and covariates as in a)).

Hypotheses are the same as for the primary outcome.

Plans for Aim 3.

To investigate the feasibility and adherence to wearable device (single-channel EEG during the night).

a) The proportion (percentage and 95% confidence interval) of participants with at least four hours of EEG recording in the first night.

b) The proportion (percentage and 95% confidence interval) of participants with at least four hours of recorded nocturnal data for each of all three nights.

Plans for Aim 4.

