To evaluate the effect of gamma-tACS compared to control stimulation on sleep EEG. Differences (individual level and group level, statistical tests as mentioned above) of sleep latency (minutes from lights out to sleep onset), sleep efficiency (sleep duration in relation to time spent in bed), sleep spindle frequency (maximum number per hour) and slow wave activity (maximum minutes of slow wave sleep per hour).

The statistical method will be the same as for Aim 2.

Null hypothesis: Sleep EEG does not change after gamma-tACS compared to the night after control stimulation.

Alternative hypothesis: There is a higher amount of sleep spindles and/or slow wave sleep after gamma-tACS (compared to the control).

Plans for Aim 5.

To investigate whether there is a correlation (Pearson's) between the stimulation-induced changes in cognitive testing scores and sleep EEG features after gamma-tACS versus after control stimulation (on individual and group level). This is an exploratory analysis.

Plans for Aim 6.

Comparison of cognitive test results after stimulation and sham on individual and group level using ANCOVA (see CT.gov). This is an exploratory analysis.

Plans for Aim 7. To investigate whether there is a correlation (Pearson's) between the stimulation-induced changes in motor activity features (according to the wristband accelerometer results) after stimulation in general and after gamma-tACS versus after control stimulation (on individual and group level). This is an exploratory analysis.

Plans for Aim 8.

To investigate whether there is a correlation (Pearson's) between the motor threshold (TMS) and the subjective symptoms during tACS. This is an exploratory analysis.

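### The Aim 2 next-day recall model uses a baseline that the schedule does not contain and handles order only as a covariate; one period-adjusted contrast should be named

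*Combined protocol and SAP*

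**What the plan says.** Section 8.3, Aim 2 a), makes recall on the day after encoding the primary outcome. The null is "There is no difference between tACS and control stimulation for ultra-delayed memory recall one day after stimulation". The model may have one or two factors: it is described "with time (baseline and post-treatment) and treatment (control vs gamma-tACS) as within-subjects factors", and with "the order in which tACS will be applied (tACS-sham or control tACS) as covariate". Bonferroni-corrected post-hoc tests follow. Section 3.2 names a paired t-test or a non-parametric test for the same comparison. Section 8.1 allows further covariates that it does not list, and calls any non-significant result inconclusive.

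Part b) of the same plan compares "visit 1-visit 2 and visit 3-visit 4; comparison of absolute results of visit 1 versus visit 3 and visit 2 versus visit 4". Aim 1 places the two sessions differently: "after both stimulation sessions, i.e. visit 2 and visit 4". Section 7 has stimulation at Visits 2 and 5, and Visit 4 is a telephone call. For Aim 4, section 8.3 says: "The statistical method will be the same as for Aim 2".

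**The concern.** A two-factor model with a baseline level needs a memory score taken before each stimulation. If none exists, the only candidate is the score from the session itself, which is obtained during stimulation. The time-by-treatment term then measures change from session to next day, and the treatment main effect averages the two occasions. Neither is the difference in next-day recall that the null describes, and the plan does not say which term will be read. The same data could be called significant or inconclusive depending on that choice.

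The second issue is period. List version 1 is always used at Visit 2 and version 2 always at Visit 5, so list difficulty and practice both fall into the period effect. Sequence is set by simple randomisation (sections 4.2 and 5.6), so equal groups are not guaranteed. Order is constant within a person, so as an additive covariate it leaves the within-person contrast unchanged.

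**Working it through.** **1. Is there a baseline?** Visit 1 (section 7.3) lists questionnaires and the MoCA, which is a single screening score common to both conditions. In the table of events (7.1), cognitive testing starts at Visit 2. Table 1 (4.3) starts RAVLT and word pairs on the stimulation day of each condition. Section 6 states: "The stimulator will be triggered by remote control from the experiment script and will administer stimulation during each single test". So no pre-stimulation score of either outcome exists. Table 1 also lists the session scores for covariate use.

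**2. The plan's own figure.** Section 5.1 gives 28 completers for dz = 0.5, power 0.80 and alpha 0.05. By the noncentral t for a paired test, 27 are needed one-sided (power at 28: 82%) and 34 two-sided (power at 28: 72%). So 28 is reproduced one-sided only. As one of two Bonferroni post-hoc tests, two-sided power is 61%.

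**3. What each term tests.** Let N and S be the gamma-minus-control differences next day and at the session, in SDs of N. Assume SD(S) = 1 and correlation ρ from 0.3 to 0.7; the documents give neither. Mean N = 0.5 and mean S = 0.5 × share, where share is the fraction of the effect already present at the session. Each test has df 27 and noncentrality √28 × mean/SD.

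- Next-day: mean 0.5, SD 1.
- Time-by-treatment (N − S): mean 0.5(1 − share), SD √(2 − 2ρ).
- Main effect ((N + S)/2): mean 0.25(1 + share), SD √(2 + 2ρ)/2.

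Example with share 0.5 and ρ = 0.5: time-by-treatment 0.25/1 gives 25%; main effect 0.375/0.866 gives 60%.

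| Share at session | Next-day | Time-by-treatment | Main effect |
|---|---|---|---|
| 0 (overnight only) | 72% | 58–91% | 28–35% |
| 0.5 | 72% | 19–38% | 55–66% |
| 0.8 | 72% | 7–10% | 70–81% |
| 1 | 72% | 5% | 79–88% |

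In 100,000 simulated trials per cell, the next-day and time-by-treatment tests disagree on significance in 27–30% (share 0), 46–55% (0.5) and 70–72% (1). The next-day test and the main effect disagree in 39–44%, about 19% and 12–19%.

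If the stated null is true but the session difference is 0.5, the time-by-treatment test rejects in 58–91% of trials, in the direction against gamma. The main effect rejects in 28–35%. The next-day test rejects in 5%.

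Using the session score as a covariate for next-day recall gives 75–94%, 56–60% and 16–38% power at shares 0, 0.5 and 1.

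**4. Period.** Each difference is d = τ ± π + e, with e of SD 1 and π the Visit 2-to-Visit 5 shift (assumed). At an 18:10 split the unadjusted bias is π × (18 − 10)/28. A split at least that uneven has probability 0.185 under simple randomisation; an exact 14:14 split has probability 0.149.

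| π (SD) | Power, unadjusted | Power, adjusted | Bias at 18:10 | Type I error, unadjusted, at 18:10 |
|---|---|---|---|---|
| 0.25 | 70% | 71% | 0.07 | about 6% |
| 0.5 | 63% | 71% | 0.14 | about 8% |
| 1.0 | 43% | 71% | 0.29 | about 10% |

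Powers are averaged over simple randomisation. Averaged that way, the unadjusted bias is 0.00 and type I error is 5%.

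**5. Does the order covariate adjust?** One simulated data set (18:10, true effect 0.5, shift 1.0) was fitted with mixed models. The treatment estimate was 0.177 without order and 0.177 with additive order. It was 0.480 with a period term and 0.480 with order-by-treatment coded −0.5/+0.5. With order-by-treatment coded 0/1 it was −0.580, because the treatment term then refers to one sequence only.

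**The case against.** The outcome and null are fixed on next-day recall. The one-factor option tests that null, and so does a post-hoc next-day comparison within the two-factor model. Because Aim 4 reuses the method, the two-factor form may be meant for outcomes that do have an earlier value. That reading is fair, but the text does not state it, names neither option as primary, and section 3.2 names a third analysis.

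On period, an additive order term would do nothing for the treatment test. Many repeated-measures routines cross a between-person covariate with the within-person factors, which with centred or factor coding would adjust for period. This also stands: the plan does not rule out adjustment, it fails to specify it. The unadjusted powers describe one reading.

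The ranges rest on assumptions. If SD(S) is 0.6 to 1.5 times SD(N), the overnight-only range for time-by-treatment widens from 58–91% to 38–94%. The alternative is directional; read one-sided in favour of gamma, the time-by-treatment rejections under a true null almost vanish (below 0.01%), while the main effect's rise to 40–48%. These points change the sizes, not the mismatch with the null.

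The list-version argument does not carry over to sleep or to letter fluency, where the same letters return. Finally, section 9 ties the primary outcome to feasibility, and section 2.2 says a memory effect is not required for the later RCT. That limits the weight of the point.

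**Conclusion.** The concern holds. The absence of any pre-stimulation memory score is plain from the schedule, and the two-factor terms do not address the stated null. No term is uniformly the most powerful: time-by-treatment can beat the next-day test when the effect arises only overnight and loses nearly all its power when the effect is already present at the session; the main effect does the reverse. That is the reason to choose before the data are seen.

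For period, the cost is power on average, plus bias in a trial that has both an uneven split and a real shift. At a 0.25 SD shift the power cost is about one point; it matters at 0.5 SD and above. The size of any shift, the correlation, the SD ratio and the share are assumptions. This should be corrected, but the feasibility conclusions do not depend on it.

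**What to change.** State one primary analysis of next-day recall (Visits 3 and 6): the gamma-minus-control difference adjusted for sequence, estimated as the mean of the two sequence means, or the equivalent model with treatment, period and participant. In a simulated 18:10 data set the two gave the same estimate (0.404, SE 0.190). Include no time factor and no covariate measured under stimulation. Apply it to RAVLT words and to word pairs, and analyse the session scores (Visits 2 and 5) as separate outcomes. Align section 3.2, and correct the visit labels throughout 8.3, including Aim 1.

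Use the same period adjustment for Aims 4 and 6, where practice or familiarity with the procedures could also produce a shift. For Aim 4, do not treat the first night as a true baseline. The synopsis describes it as acclimation ("Eligible participants will first collect sleep EEG at home for one night to acclimate to the data collection during sleep"), and a single value per person cancels from the within-person contrast.

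The cost is SAP wording. With no period shift, two-sided power falls from 72.4% to 70.6% under simple randomisation, and from 72.3% to 72.1% at 14:14. If the effect arises only overnight and ρ = 0.7, the plan also gives up the time-by-treatment term's 91% for 72%; that term can be reported as secondary. Which of the two scores is primary, and whether the test is one- or two-sided, also need stating; this change settles neither.

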| Numbers of Enrollees | This pilot study requires n = 28 participants who complete all aspects of the protocol. Participants are recruited and enrolled until this target is reached. We anticipate screening up to 100 participants and enrolling up to 50 participants. |

| | |
|--|---|
| Intervention | 
This is a single-center prospective interventional control controlled cross-over pilot study.
 
The intervention consists of the application of tACS stimulation in the gamma-frequency range during approximately one hour of cognitive testing.
 |
| Outcome Measures | 
Aim 1: Cognitive testing during tACS completed in >80% of participants.
 
Aim 2: Participants will memorize 15 words ("Rey Verbal Learning Test", (a)) and 8 word-pairs (associative verbal memory, (b)) during gamma-tACS and control tACS. They will be required to recall the words after a short delay on the same day, on the day after and after 5 days ("ultra-delayed recall"). The number of correctly remembered words (a) and word-pairs (b) will be recorded.
 
Aim 3: Feasibility (a) will be considered feasible if the device has been worn for at least 4 hours during the first night for >/= 80% of participants. Acceptability (b) will be considered as given if the device has been worn for at least 4 hours during each of the three nights in >/=80% of participants.
 
Aim 4: Amount of sleep spindles (a) and slow wave sleep (b) during sleep recording.
 
Aim 5: Exploration of correlation between memory recall performance and sleep EEG features (especially spindles, slow waves). Difference in recall scores (verum versus sham tACS) will be correlated with differences in sleep EEG features (verum versus sham tACS).
 
Aim 6: For (a) the number of correct words, of perseverations and of rule breaks will be calculated. For (b) and (c) time for test completion and errors will be calculated. For (d) percentile ranks for the following subtests will be calculated: Alertness, Go/NoGo, Divided Attention, Visual Scanning.
 
Aim 7: Exploration of correlation between amount of motor activity/inactivity phases (measured by actigraphy watch) and stimulation versus no stimulation as well as gamma- versus control stimulation.
 
Aim 8: Exploration of correlation between the TMS motor threshold and the maximal tolerated amplitude (according to the subjective symptoms) for tACS.
 |

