| Aim 3: Investigate feasibility (a) and acceptability (b) of wearable device (single-channel EEG during the night) | Fraction of participants wearing the device on (a) the first and (b) all three nights planned according to the protocol. | Proportion of participants having worn the device during (a) the first and (b) all three nights for at least four hours each night | Observed proportion and 95% C.I. |
| Aim 4: Evaluate the effect of gamma-tACS on sleep spindles (a) and slow wave sleep (b) compared to sham stimulation | Amount of sleep spindles (a) and slow wave sleep (b) after tACS-stimulation and control stimulation. | Differences (individual level and means) of sleep spindle frequency (maximum number per hour) and slow wave activity (maximum minutes of slow wave sleep per hour) | Comparison between results after gamma-tACS and control tACS on individual and group level (mean differences, components of variance, regression coefficients) |
| Aim 5: To investigate whether there is a correlation between memory recall and sleep EEG | Memory and associative memory recall performance; EEG features (as for aim 4) | Correlation between changes in memory recall and sleep EEG (amount of spindles and slow wave sleep) for gamma- versus control tACS | Exploratory investigation of correlations (Pearson's) between stimulation induced changes in memory recall performance and sleep EEG features |
| Aim 6: To investigate the effect of stimulation on different cognitive functions, i.e. a letter fluency task (a), executive functioning (Stroop Test (b), Trail Making Test (c)) and attention | Effect of tACS and control stimulation on cognitive testing during and on the day after stimulation. | For (a) the number of correct words, of perseverations and of rule breaks will be calculated. For (b) and (c) time for test completion and errors will be calculated. For (d) percentile ranks for the following subtests will be calculated: Alertness, Go/NoGo, Divided Attention, Visual Scanning | Comparison between results after stimulation and sham on individual and group level (mean differences, regression coefficients, components of variance) |

| (Attentional Performance, TAP (d)) | | | |
|--|--|--|---|

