4.2. Experimental Design

This is a controlled cross-over study. Participants will be randomly allocated to the respective sequence (first tACS, then control stimulation – vice versa) via simple randomization, i.e. based on a single sequence of random sequence numbers generated by computer.

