Visit 5 (6-9 days after Visit 2; afternoon/early evening, i.e. start between 12pm and 6pm)

The day before: reminder (e-mail/SMS/phone call, depending on the participant's preference) of appointment on the following day - including request to abstain from alcohol and drugs as well as from excessive caffeine consumption.

1. Questioning whether there has been any use of alcohol, psychotropic substances or illicit drugs during the past 24 hours. If yes, the participant is excluded.
2. Questioning if there is a new diagnosis. If yes, the participant will be excluded if the diagnosis meets exclusion criteria.
3. Questions to assess current sleepiness and mood, as this may affect the results of further testing:
 - 3.1 Questions for sleep quality the night before
 - 3.2 Karolinska Sleepiness Scale
 - 3.3 Positive And Negative Affect Schedule (PANAS)
4. Gamma-tACS or controlstimulation (according to randomization) during the following cognitive tests, presented on a computer screen (2 minutes of resting EEG without stimulation after each test):
 - 4.1 Rey Auditory Verbal Learning Test (RAVLT, version 2)
 - 4.2 Letter Fluency; letters F, A, S

- 4.3 Stroop Color and Word Test
- 4.4 Trail Making Test A and B
- 4.5. Word association test; version 2
- 4.6 Four subtests of the Test of Attentional Performance (TAP): Alertness, Go/NoGo, Divided Attention, Visual Scanning
- 4.7 RAVLT delayed recall; version 2
5. Evaluation of side effects with open question (“Did you feel anything particular or note anything special during this session?”)
6. The participant will be given the sleep diary for the third night with the EEG headband.

Visit 6 (day after Visit 5; morning, i.e. start between 8am and 12pm)

1. The participant brings back the EEG-headband (used the night before). Data quality check, review of sleep diary.
2. Questioning whether there has been any use of alcohol, psychotropic substances or illicit drugs during the past 24 hours. If yes, the participant is excluded.
3. Questions to assess current sleepiness and mood, as this may affect the results of further testing:
 - 3.1 Questions for sleep quality the night before
 - 3.2 Karolinska Sleepiness Scale
 - 3.3 Positive And Negative Affect Schedule (PANAS)
4. Cognitive follow-up testing
 - 4.1 RAVLT “ultra-delayed” recall; version 2
 - 4.2 Letter fluency; letters B, H, R
 - 4.3 Stroop Color and Word Test (SCWT)
 - 4.4 Trail Making Test Part A and B
 - 4.5 Word association recall; version 2

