8.1. Strategies that Apply to all the Aims

All testing described below assumes a significance threshold of $p = 0.05$. Analyses will be deemed to be statistically significant if the p-value is less than this threshold. An analysis that does not exceed this threshold will be considered inconclusive. The proposed statistical analysis strategy acknowledges that no p-value can reveal the plausibility, presence, truth, or importance of an association or effect.

There may be additional covariates included in the analysis. Data will be assessed for normality and, if deemed necessary, corrective procedures will be applied (e.g., log normalization). This correction will be applied upon consideration of the variables themselves, and not based on the result of the intended analysis.

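### Aim 5 correlates gamma-minus-control differences without adjusting for sequence, so Pearson's r is biased if recall and sleep EEG both have a period effect

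*Combined protocol and SAP*

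**What the plan says.** Section 8.3 defines the Aim 5 analysis as a "correlation (Pearson's) between the stimulation-induced changes in cognitive testing scores and sleep EEG features", comparing gamma with control stimulation, and labels it exploratory. The synopsis (Outcome Measures, Aim 5) states what enters the correlation: "Difference in recall scores (verum versus sham tACS) will be correlated with differences in sleep EEG features (verum versus sham tACS". The aims table in section 3 gives the same target: "Correlation between changes in memory recall and sleep EEG (amount of spindles and slow wave sleep) for gamma- versus control tACS". None of these places mentions order, sequence or period.

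Elsewhere the plan does treat order as something to adjust for. The Aim 2 model includes treatment and time "and the order in which tACS will be applied (tACS-sham or control tACS) as covariate". Aim 4 inherits this: "The statistical method will be the same as for Aim 2". Aim 5 has no such sentence. Table 1 (section 4.3) lists sleep latency and sleep efficiency for covariate use in Aim 5, but no sequence variable. Section 8.1 adds only that "There may be additional covariates included in the analysis", without naming order or Aim 5.

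Sequence is allocated "via simple randomization, i.e. based on a single sequence of random sequence numbers generated by computer". Section 7.4 gives every participant version 1 of the RAVLT and of the word-pair test in the first stimulation period, and version 2 in the second.

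**The concern.** A participant's gamma-minus-control difference contains the treatment effect and also the difference between periods. The period part has one sign for those who receive gamma first and the opposite sign for those who receive control first. If recall and the sleep feature both shift between periods, the two differences move together across the sequence groups even when nothing links them within a group. An unadjusted Pearson coefficient counts that movement as association.

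At stake is the trial's one look at whether changes in sleep track changes in memory. Period effects of matching direction could suggest a link that reflects only which condition came first. Period effects of opposite direction could hide a real one.

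The schedule leaves room for a period effect on each side. For recall, list version is completely confounded with period, and by Visit 5 participants have already met next-day and five-day recall testing. For sleep, the Visit 2 night directly follows the first headband night, while the Visit 5 night comes after a gap of several days, so some residual adaptation to the headband is possible.

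**Working it through.** **The plan's own figures.** The documents state no power or sample size for Aim 5. The only figure used here is n = 28 (sections 5.1 and 9). It is reproduced one-sided: the exact binomial test of 50% against 80% completion first reaches 95% power at n = 28 (reject at 19 or more, alpha 0.0436, power 0.961), and a one-sided paired t-test at dz = 0.5 needs 27 for 80% power. Nothing below depends on how 28 was reached.

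**Inputs.**
- From the documents: n = 28, two sequences, simple randomization, threshold 0.05 (sidedness not stated; two-sided used here), plain Pearson correlation.
- Assumed, because the documents give neither period-effect sizes nor SDs: the period shifts dm (recall) and ds (sleep). Each is half the gap between the two sequence means of the gamma-minus-control difference, in units of its within-sequence SD.

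**Model.** With s = +1 for one sequence and −1 for the other:

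recall difference = treatment effect + dm·s + error

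sleep difference = treatment effect + ds·s + error

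With equal expected sequence numbers and within-sequence correlation ρ, the unadjusted coefficient estimates

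r = (ρ + dm·ds) / √[(1 + dm²)(1 + ds²)]

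With ρ = 0 the numerator is the product dm·ds, so r is zero whenever either shift is zero.

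**Worked cases with ρ = 0.**
- 0.25/0.25: 0.0625 / 1.0625 = 0.06
- 0.5/0.1: 0.05 / √(1.25 × 1.01) = 0.04
- 0.5/0.25: 0.125 / √(1.25 × 1.0625) = 0.11
- 0.5/0.5: 0.25 / 1.25 = 0.20
- 0.75/0.75: 0.5625 / 1.5625 = 0.36
- 1/1: 1 / 2 = 0.50

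**False-positive rates.** These come from simulation with n = 28, simple randomization, at least 100,000 runs per case and a nominal 5% test.

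| dm / ds | Induced r | Rejection, unadjusted | Rejection, partial given sequence |
|---|---|---|---|
| 0.5 / 0 | 0.00 | about 5% | about 5% |
| 0.25 / 0.25 | 0.06 | about 6% | about 5% |
| 0.5 / 0.1 | 0.04 | 5.5% | about 5% |
| 0.5 / 0.25 | 0.11 | about 8% | about 5% |
| 0.5 / 0.5 | 0.20 | 17% | about 5% |
| 0.5 / −0.5 | −0.20 | 17% | about 5% |
| 0.75 / 0.75 | 0.36 | 49% | about 5% |
| 1 / 1 | 0.50 | 84% | about 5% |

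Exactly 14 per sequence gives almost the same rates (18% at 0.5/0.5, 86% at 1/1), so balancing the allocation would not remove the bias.

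**Masking.** With ρ = 0.4, dm = 0.75 and ds = −0.75, the formula gives (0.4 − 0.5625) / 1.5625 = −0.10. The simulated mean is −0.11. The partial correlation averages 0.39.

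**Price of adjusting when it is not needed.** With ρ = 0.4 and no period effects, power is 0.58 unadjusted and 0.56 adjusted.

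**The case against.** The best case against the point is that it needs two period effects and the documents demonstrate neither.

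- **Recall.** A reader might infer from the fixed list order that recall must have a period effect. It does not follow. Confounding of version with period makes an effect possible, but nothing in the documents says that the two lists differ in difficulty, and a new list limits item-specific practice.
- **Sleep.** The synopsis provides an acclimation night before any stimulation. The two nights compared are therefore the second and third with the headband, and the first-night effect is already outside the contrast. Later adaptation is conjecture.

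This objection stands, and it limits the size of the problem. A shift of 0.5 SD in each outcome means that both period effects are as large as the treatment effect used in section 5.1 (dz = 0.5). A shift of 1 SD in each is twice that. If the acclimation night leaves only 0.1 SD for sleep, the rejection rate is 5.5% even with 0.5 SD for recall.

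The stakes are also low. Aim 5 is exploratory, section 2.2 says that effects on memory and sleep are not needed to go on to a full trial, and section 8.1 disclaims reading truth from a p-value. This stands as a limit on severity. It does not make the unadjusted coefficient preferable, because the exploratory label does not remove bias. The optional covariate clause in section 8.1 does not commit the plan to adjusting Aim 5.

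A reader might also carry the point over to Aim 7. The documents do not support that. The synopsis relates activity to stimulation condition, and the aims table correlates the day before with the day after stimulation. Neither pairs two gamma-minus-control differences, so the shared-sequence mechanism is not shown to apply.

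**Conclusion.** The point holds in a limited form. As written, Aim 5 omits an adjustment that the plan makes for the same two outcomes in Aims 2 and 4, and the omission biases Pearson's r whenever recall and the sleep feature both have a period effect. The bias can go in either direction.

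Its size is unknown because it depends on period shifts that the documents do not give. It is negligible at 0.25 SD in each outcome or below, moderate at 0.5 SD in each, severe at 0.75 SD or more in each, and absent if only one outcome shifts. The calculations assume normal errors, equal expected sequence numbers and a two-sided test. It would go too far to say that the plan will produce a false sleep-memory link: the documents make one possible, not likely. No primary or secondary conclusion and no sample-size argument depends on Aim 5. This is a low-cost improvement to an exploratory analysis.

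**What to change.** In section 8.3, Plans for Aim 5, state that each correlation between gamma-minus-control differences will be a partial Pearson correlation given treatment sequence, tested on n − 3 degrees of freedom (25 at n = 28). Repeat this in the synopsis and the aims table.

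Centring each difference on its sequence mean gives the same coefficient. The test must still use n − 3: an ordinary Pearson test on centred data, with n − 2, rejects about 5.5% rather than 5%.

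The cost is one sentence and one degree of freedom, which is a power of 0.56 instead of 0.58 for a true correlation of 0.4 when there are no period effects. No extra data, visits or participants are needed, and no change to Aim 7 is asked for.
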